The general aim of this study is the development of the optimal algorithm for the management of all adnexal masses. This can be broken down into different specific objectives: 1) to study the occurrence of complications such as rupture, torsion, or malignancy in patients with benign looking conservatively treated masses; 2) to test the published IOTA diagnostic models for predicting that a mass is malignant at first visit or benign (either on the basis of histology following surgery or by the absence of malignant features on an ultrasound scan one year after the initial visit), and to predict complications (e.g. ocurrence of malignancy and other) during long-term follow-up; 3) to investigate factors that may be related to the need for surgery during long-term follow up; 4) to study the natural history of conservatively treated benign looking masses and to establish descriptive curves of the longitudinal changes seen in parameters from conservatively managed benign tumors (e.g. change in diameter, size of any solid component, number of papillations, or color score). We hope these curves will allow us to determine if any particular growth pattern is associated with complications or malignancy

Related to these four objectives, we aim to carry out the following analyses: 1) descriptive analysis of complications overall and by participating center (anonymised) and overall Kaplan-Meier curves for the need for surgery among benign looking masses; 2) estimation of discriminatory ability of LR1 for malignancy at the initial visit using the c-index and ROC curves and for complications during long-term follow-up using the hazard ratio and c-index within the context of survival analysis; 3) survival analysis to investigate predictors of the need for surgery during long-term follow-up of non-operated masses; 4) the development of longitudinal curves of the changes seen in the characteristics of non-operated masses using longitudinal analysis techniques such as mixed models and functional linear discriminant analysis (FLDA).

Methods

Study design

International multicenter prospective observational cohort study

Eligible for inclusion

- Any woman at least 18 years old with an adnexal mass.
- Any mass with benign ultrasound morphology may be suitable for conservative management.
- Pregnant patients can be included, but their data will be analysed separately.

Exclusion Criteria

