- Cysts that are deemed to be clearly physiological and less than 3 cm in maximum diameter are not eligible for inclusion.
- Any cyst with features of malignancy is excluded from the conservative management
- The denial or withdrawal of oral informed consent

Official approval by the Ethics Committee

The multicentre project IOTA phase 5 will be submitted to the Ethics Committee of the University Hospitals Leuven as main investigating centre as well as in each participating centre. The study will be performed in accordance with generally accepted standards of Good Clinical Practice and the investigators will adhere to all applicable laws and regulations governing the conduct of clinical trials, including but not limited to the ICH Harmonized Tripartite Guidelines for Good Clinical Practice and the Declaration of Helsinki (2008).

Insurance policy

This multicentre international study is initiated by the University Hospitals Leuven, Belgium. Each participating centre outside Belgium is fully responsible for patient care within its own hospital in agreement with local laws. Each centre is also responsible for all legal aspects of patient care and for its own insurance for all matters related to this study.

Financial Support

The IOTA phase 3 project is supported by an Applied Biomedical Research grant (Toegepast Biomedisch Onderzoek, TBM) from the Flanders Institute for Scientific and Technological Research: IWT Flanders, Belgium (IWT-TBM 070706). This grant covers costs of central data collection, proteomic analysis, analysis of new tumour markers and statistical analyses. For IOTA phase 5 we received a research grant for a doctoral researcher by the Flemish Fund for Scientific Research (FWO Vlaanderen 06260, IOTA5).

There is no financial compensation for principal investigators nor patients.

Definition of benign ultrasound morphology

This is defined on the basis of subjective assessment of ultrasound findings by an experienced ultrasound examiner. Only lesions where the ultrasound examiner is certain or almost certain that the lesion is benign can be managed conservatively. The management of benign masses will be decided according to local protocols.

Number of study patients and recruitment period

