This is an observational study and therefore a sample size cannot be calculated. We aim to collect at least 3000 women with an adnexal mass and at least 1000 women with an adnexal mass managed conservatively. We plan an initial recruitment period of eighteen months. Patients will be followed up for at least 5 years, unless surgical intervention is necessary.

Follow-up

Ultrasound (and clinical) follow up will be organised by the ultrasound examiner who entered the patient into the study. Follow-up will be after 3 months (maximal range 1-4 months), 6 months (maximal range 4-8 months) and then every 12 months (maximal range 10-14 months). Although measurement of serum CA 125 levels is encouraged, it is not mandatory for inclusion in the study. If CA125 is measured it should be recorded in the study screen and preferably measured on each visit.

Duration of follow-up

A yearly analysis will be carried out in order to evaluate acute complications. The duration of follow up will be for at least 5 years and is not limited as long as the patient is compliant with the study and the study is ongoing.

Departments (e.g. radiology departments) that are not involved with clinical decision making about plans for follow up or surgery cannot participate in the full IOTA 5 study. In these centres data can be prospectively collected as an observational study. Only patients with appropriate outcome measures (i.e. follow up ultrasonography after one or more years or patients with complete details of clinical history or surgical procedures) will be included in any statistical analysis.

Collection of clinical data

Family history: Number of first degree relatives with ovarian cancer (0-...)

Medical history:	Personal history of ovarian cancer and breast cancer
	Age (years)
	Previous hysterectomy (yes/no)
	Previous oophorectomy (yes/no)
	Contraception (drop down list) (None/oral combined contraceptive
	pill/progestogen only pill/ patch/vaginal ring/Mirena coil/copper IUD)
	Hormonal therapy (yes, no).
	Is the patient currently wishing to conceive? (yes/no)
	Menopausal status (pre- or postmenopausal)
	History of subfertility? Yes/no
	History of ovarian stimulation for subfertility? Yes/no
For ALL path	ents before menopause two extra questions pop up:

Patient is currently pregnant? (No/Yes)

Patient became pregnant during the last year? (No/Yes)

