• If Yes: Outcome of pregnancy (it should be possible to enter more than one date, should there be more than one pregnancy during follow-up):

- Ongoing pregnancy
- Miscarriage; date: ...
- o Ectopic; date: ...
- o Termination; date: ...
- o Delivery; date: ...
- Complications from the lesion during pregnancy? No/Yes (pop up list):
 - Acute pain
 - Chronic pain
 - Suspected torsion
 - Infection
 - Haemorrhage related to the cyst
 - Cyst rupture
 - Required surgery
 - Other, please specify:
- Complications from the lesion during delivery? No/Yes (pop up list):
 - Acute pain
 - Suspected torsion
 - Haemorrhage
 - Cyst rupture
 - Obstructed labour
 - Malpresentation (e.g. breech or unstable lie)
 - Other, please specify:

Ultrasound examination

A standardized ultrasound examination following the IOTA protocol is carried out.

All ultrasound variables are included in the dedicated software. In the database 0 always means NO and 1 always means YES.

The adnexal lesion is that part of an ovary or of an adnexal mass that is judged by ultrasonography to be not consistent with normal physiology. This can be a persistent unilocular cyst, surrounded by normal looking ovarian stroma with some follicles. In this case the whole ovary containing the cyst is the 'ovary', whereas the unilocular cyst is the 'lesion'. Both are measured and the cyst is described as being 'unilocular' and not 'unilocular-solid'. In other cases the lesion is separate from the ovary (e.g. hydrosalpinx). Again, both ovary and lesion are measured separately. In other cases no normal ovarian stroma is seen. In these cases the lesion and the ovary are undistinguishable and the measurement of lesion and ovary will be the same.

Measurements (in mm): The ovary in two perpendicular planes

The lesion in two perpendicular planes

The volume of the tumor is calculated from the three diameters in two perpendicular planes

• The presence of ascites (*i.e.fluid outside* the pouch of Douglas) is noted (yes/no).

• Fluid in the pouch of Douglas is measured in the sagittal plane (the largest anteroposterior diameter is given).

- An incomplete septum (as seen in hydrosalpinges) is defined as a thin strand of tissue running across the cyst cavity from one internal surface to the contralateral side, butis not complete in some scanning planes. If a cyst only has incomplete septa, it is unilocular, despite the fact that in certain sections the cyst appears to be multilocular.

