- If yes : date of first complication:

- And pop up list (you can select more than one):
 - Acute pain
 - \circ Chronic pain
 - Suspected torsion
 - o Infection
 - Haemorrhage
 - o Rupture
 - $\circ~$ Other, please specify:
- Death: date
- Death directly or indirectly relatd to adnexal mass?
- cause of death (

• Autopsy findings: specify:

Not needed for IOTA phase 5: second stage tests

Consent / information leaflet

Information leaflets are at the discretion of the participating centres. Approval of the local Ethical Committee for clinical studies is necessary.

Serum tumour markers

Serum CA 125 measurements or other tumour markers are performed locally, using a CA 125 II immunoradiometric assay

Tissue collection

Preferably the whole tumour should be removed. However, representative biopsies may be sufficient (e.g. in advanced ovarian cancer or endometrioma).

Tumour classification

Tumours are classified according to the criteria recommended by the International Federation of Gynecology and Obstetrics (FIGO). In malignant tumours the degree of differentiation is included.

Statistical analysis

For the first objective, a descriptive analysis of complications on all data and stratified for participating center (anonymized) will be performed, as well as an overall Kaplan-Meier curve of 'complication free survival'. Complication free survival is defined as the time to the need for surgery during long-term follow-up. Patients that did not need surgery at the end of the follow-up period are right censored at the time of the last examination.

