IOTA5 interim analysis

Statistical Analysis Plan

Page 2-11: Follow-up study (27 December 2017)

Page 12-19: Performance of models for ovarian tumor diagnosis when applied to all patients (operated or conservatively followed) (28 May 2019)

IOTA5 interim analysis

Follow-up study

Statistical Analysis Plan

27 December 2017

1.1 Data:

The IOTA5 database will be used for the analysis and the following in- and exclusion criteria will be used.

Inclusion criteria:

- Initial policy is conservative management,
- The mass was diagnosed as benign at the first visit (i.e. subjective assessment = benign AND certainty = certainly benign OR probably benign).
- First scan between 1 January 2012 and 1 March 2015.

Exclusion criteria:

- Patients who did not give consent; data from patients who withdrew consent during the study will not be used either
- Younger than 18 years at first scan
- Cysts that are deemed clearly physiological and less than 3 cm in maximum diameter are not eligible for inclusion. [*We identified 13 such patients in the database for the interim analysis.*]

Further issues regarding data:

- Patients who underwent surgery for the adnexal mass after the first scan, despite the initial policy being conservative management, will be used in descriptive statistics but not in the main survival analysis. We will include them in a sensitivity analysis (cf below).
- Patients who withdrew consent during the study will not be used
- Only the dominant mass of the patient will be included
- We include follow-up data up to 30th of June 2017 such that all patients should have been followed up for 24 months (protocol allows +/- 2 months, hence this date allows 26 months follow-up for all patients; for the survival analysis, we use all available data (i.e. also information on the first scan after 26 months if available) but only show results up to 30 months. 30 months implies 2.5 years, this is convenient when constructing plots. Follow-up after 30 months is incomplete and hence results are uncertain.
- Although the aim of IOTA5 was to recruit patients consecutively and organize follow-up, there is a lot of heterogeneity among centers regarding adherence to the follow-up protocol. Therefore, we will perform a sensitivity analysis including all centers that have contributed to patient recruitment. However, only data of the following centers will be used for the primary analysis (centers with sufficient data quality: based on N recruited for conservative

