1.2.1 Population

The population in this study consists of cases with a new adnexal mass (not already in follow-up in the center), and of patients with a mass that was already in follow-up in the center before the center started recruitment for the IOTA5 study. The latter group is likely a selected one: known masses that have spontaneously resolved or were operated on before the center started recruiting for the IOTA5 study will not be included. In addition, follow-up of these masses before the start of IOTA5 is ignored. Therefore, we assume that the patients with a known mass already in follow-up will more likely have a persistent and harmless mass. In this group, we can expect fewer spontaneous resolutions, less surgery for suspicion of malignancy or other complications, resulting in fewer confirmed complications. First, we will analyze the follow-up for all patients (new + known masses) in order to describe fully what was found during the IOTA5 study. Then, we will focus on follow-up results for patients with new masses only in order to obtain statistically more correct estimates.

Patients that have been selected for conservative management after subjective assessment by the ultrasound investigator, can nevertheless undergo surgery after inclusion, before having proceeded to follow-up (because of many reasons e.g. decision of the managing clinician, patient request etcetera). In the primary analysis we will describe this group with immediate surgery (why surgery was performed, what was found at surgery), but for the survival analysis only cases with at least one follow-up scan will be included (intention to treat with follow-up). In the appendix, we will add a sensitivity analysis that involves a survival analysis including patients with immediate surgery (intention to treat with or without follow-up).

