1.2.3 Planned analyses, figures, tables

This list does not indicate which figures or tables will be included in the main document.

Figure: Flowchart of patients

Table: Patient and tumor characteristics at inclusion for patients with initial policy conservative (including patients that were operated immediately). *The list of variables to be described can be augmented with other relevant variables according to clinicians, and these will be added irrespective of the results.*

	All patients	Patients with newly detected masses	Patients with masses already in follow-up
Age			
Menopausal status			
Time in follow-up before inclusion		NA	
Tumor type			
Lesion size			
Solid parts			
...			
Presumed diagnosis (endometrioma etc)			
...			
Subjective assessment (certainty)			
Immediately operated			
Patients with a newly detected masses, n (%)		NA	NA
Symptomatic at first scan			
Pain			
Abnormal bleeding			
Other symptoms			
Outcome events			
Cyst spontaneously resolved			
Surgery performed			
Invasive tumor			
Borderline tumor			
Cyst torsion			
Cyst rupture			
Complications detected at surgery*			
No complication detected at surgery			
Patient died			

Table: List of centers, with number of patients per center. This table will include all centers (all the ones included in the sensitivity analysis). Order by total number of patients (conservative and surgery). This table is intended to be included in the appendix or supplementary material.

Center	N	Initial policy surgery	Initial policy conservative	% No info	% Useful info
Malmo, Sweden					
Leuven, Belgium					
Rome, Italy					
...					
All oncology centers					
All non-oncology centers					
All centers					

Useful information: study outcome observed, or follow-up of at least 10 months.

Table: List of centers, with number of patients per center. This table will include centers with sufficient data quality (all the ones included in the primary analysis). Order by total number of patients (conservative). This table is intended to be included in the main report.

Center	Initial policy conservative	% Useful info
Malmo, Sweden		
Leuven, Belgium		
Rome, Italy		
...		
All oncology centers		
All non-oncology centers		
All centers		

Figure: Histogram of time of follow-up before recruitment in IOTA5 for patients with a mass already in follow-up at inclusion ('old' patients)

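### Do the two interim SAPs need their own rule for pregnant patients, whose data the protocol says are analysed separately?

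*Protocol*

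**What the plan says.** The protocol, under Eligible for inclusion, states: "Pregnant patients can be included, but their data will be analysed separately". Under Collection of clinical data it equips that rule. For every woman before menopause the study screen asks about current pregnancy and pregnancy in the past year, then about the outcome of the pregnancy and about complications from the lesion during pregnancy and delivery. The outcome item is built for repeated events: "it should be possible to enter more than one date, should there be more than one pregnancy during follow-up".

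The protocol's Statistical analysis section does not mention pregnancy. For the first objective it plans "a descriptive analysis of complications on all data and stratified for participating center".

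The follow-up SAP lists its criteria in section 1.1, its population in 1.2.1, its subgroups in 1.2.2 and its tables in 1.2.3. The model-performance SAP lists its population and criteria in 1.2 and 1.3, its imputation variables in 1.5.1, its subgroups in 1.5.7 and its sensitivity analyses in 1.5.8. Pregnancy appears in none of these places.

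**The concern.** The protocol makes an unconditional statement about how one group's data are handled, and neither analysis plan takes it up. The contrast with other rules is plain. The protocol says "Cysts that are deemed to be clearly physiological and less than 3 cm in maximum diameter are not eligible for inclusion"; both SAPs repeat this, and the follow-up SAP adds "We identified 13 such patients in the database for the interim analysis". Nothing comparable is said about pregnant women.

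Read literally, the criteria in both SAPs would let women pregnant at the inclusion scan into the main cumulative-incidence and model-performance estimates. The word for separate analysis is also open: it could mean removal from the main set or an additional report. If that choice were made with the data in hand, it could in principle be steered by the results. The study's outcomes (surgery, torsion, rupture) overlap with the complications recorded in pregnancy, so the group is not obviously irrelevant to the endpoints.

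**Working it through.** **Step 1: is the omission real?** The six eligibility bullets of the protocol, set against the SAPs:

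| Protocol bullet | Follow-up SAP | Model-performance SAP |
|---|---|---|
| Adult with an adnexal mass | 1.1 | 1.2, 1.3 |
| Benign morphology may be managed conservatively | 1.1 (diagnosed benign at first visit) | none |
| Pregnant patients | none | none |
| Small physiological cysts excluded | 1.1 | 1.2, 1.3 |
| Features of malignancy bar conservative management | 1.1 (diagnosed benign at first visit) | none |
| Consent | 1.1 | 1.3 |

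Five of six have a counterpart in at least one SAP, three of six in both, and pregnancy in neither. The omission is confirmed.

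**Step 2: do the SAPs decide to pool these women?** The phrases that seem to say so contrast other things. In the protocol, all data is set against results by centre. In section 1.2.1 of the follow-up SAP, "we will analyze the follow-up for all patients (new + known masses" is set against new masses alone. In section 1.1 of the model-performance SAP, the population is spelled out as operated plus conservatively managed patients. None of these is a decision about pregnancy. The count of 13 is not a parallel either: it notes ineligible women found in the database, whereas pregnant women are eligible.

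**Step 3: does silence in these SAPs amount to dropping a protocol analysis?** Both are headed as interim analyses and each serves one report. They also omit, without saying that it comes later:

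- the LR1 model (the models in section 1.4 of the model-performance SAP include LR2 but not LR1), and with it LR1 as a predictor of complications in follow-up;
- the third objective (predictors of the need for surgery);
- the fourth objective (longitudinal curves).

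Silence here therefore does not show that an analysis was abandoned. A separate report on pregnant women is compatible with both plans.

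**Step 4: how would an analyst read the rule?** The sentence stands in the eligibility list and speaks of including pregnant women, so its natural reference point is pregnancy at inclusion. Pregnancies that begin later are recorded as follow-up events. Removing women because of a later pregnancy would select on information that did not exist at baseline, which a survival analyst would avoid. The remaining choice is between taking women pregnant at inclusion out of the main set and keeping them in with an additional report. Both can be done with the recorded field and the flowchart planned in section 1.2.3.

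**Step 5: what is the possible size?** The documents give no number of pregnant women, so this is a range on stated assumptions.

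- *Cohort size.* The presumed-diagnosis table in the follow-up SAP (section 1.2.2) gives counts with rounded percentages. The tightest bounds are 609 / 0.195 = 3123 and 1470 / 0.465 = 3161. The SAP does not say exactly which set the table describes.
- *Assumed share p.* At 0.5%, 1%, 2% and 5%, this means about 16, 31 to 32, 62 to 63, and 156 to 158 women.
- *Shift.* If pregnant women differ from the others by D in a cumulative incidence, pooling them moves the estimate by p × D. With an assumed D of 20 percentage points, the shift runs from 0.005 × 20 = 0.1 points to 0.05 × 20 = 1.0 points.

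Within the premenopausal subgroup the share, and so the shift, is larger by a factor of 1/q, where q is the premenopausal fraction of the cohort. The documents do not give q.

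**The case for a change.** The strongest case for a change is that an analysis rule in the protocol should be traceable in the analysis plan. This rule is unconditional, the data collection was built for it, and the follow-up SAP restates other eligibility rules as a matter of practice. Even if the separate report comes later, each SAP defines its own analysis set and could have said whether these women are in it. A few lines would settle the matter.

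Some of this stands. From the SAPs alone one cannot tell whether women pregnant at inclusion are in the main sets, and the protocol does not define the separate analysis. For rare findings, even a small absolute shift could be large relative to the estimate.

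The rest does not carry the case to a change:

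- The charge that the SAPs depart from the protocol holds only if separate analysis means removal. If it means additional reporting, keeping these women in the main analysis is no departure.
- The remedies that would satisfy the concern are opposites (exclude, keep, or defer). It asks for a choice to be written down and does not show that an analysis is wrong.
- For the rare findings, section 1.2.3 of the follow-up SAP plans a case-by-case table of confirmed malignancy, rupture and torsion, and leaves its list of parameters open. For the baseline table it says "The list of variables to be described can be augmented with other relevant variables according to clinicians", and that such additions will be made whatever the results. Neither is a separate analysis, but both leave room to show pregnancy status without amending the plan.

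**Conclusion.** No change to the plan is called for. The protocol's rule remains in force, because an interim SAP that does not mention it does not override it. The women can be identified, and the sensible reading (status at the inclusion scan, number shown, results reported apart) is available to any analyst who has the protocol. What remains is a matter of clear reporting: a reader of the results should be told how many women were pregnant at inclusion and whether they are in the main estimates.

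The effect on the pooled estimates is unknown and probably small: 0.1 to 1.0 percentage points if the share is 0.5% to 5% and the difference in cumulative incidence is 20 points. Both inputs are assumptions, and the shift would be larger within the premenopausal subgroup. The conclusion also assumes that the recorded pregnancy status refers to the inclusion visit; the documents report no fault in that field.

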For the second objective, the discriminatory ability of LR1 and the polytomous model to detect malignancy at the initial visit will be assessed. To this end, the logit of the risk of malignancy given by LR1, logit(LR1), is used to predict malignancy using logistic regression, and the performance assessed with the odds ratio, the c-index and a ROC curve. Linearity of the effect of logit(LR1) will be assessed using spline functions. This analysis is planned one year after the end of the inclusion phase of the trial. Non-operated masses will be classified as benign at the initial visit if there is an absence of a clinical diagnosis of cancer after 1 year of follow up. In addition, the ability of LR1 to predict complications during long-term follow-up will be assessed. This will be done using Cox proportional hazards regression with the logit(LR1) as predictor of complication free survival. Performance will be assessed using the hazard ratio and the c-index within the context of survival analysis. Linearity of the effect of logit(LR1) will be investigated using Schoenfeld residuals.

For the third objective, a multivariable survival analysis will be undertaken using Cox proportional hazards regression or more complex alternatives based on support vector machines (30). The models will be penalized to prevent overfitting, given that not enough events (i.e., patients that need surgery during long term follow-up) are expected for the number of available predictor variables. Internal validation will be assessed through bootstrapping rather than a split of the data in training and test sets (31).

For the fourth objective, longitudinal normative curves will be derived of the changes seen in the characteristics of non-operated masses. Longitudinal analysis techniques such as mixed models, longitudinal support vector machines, and functional linear discriminant analysis (FLDA) (32-34).

Study supervision

Central supervision: the Steering Committee is responsible for the protocol, quality control, interim analyses of the data and final analysis and reporting of the study.

Local supervision: the Principal Investigators are responsible for the data collection in their centres.

[name] is responsible for the co-ordination of the overall IOTA project and the contact between the centres.

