1.5 Statistical methods

1.5.1 Missing values for CA125 and outcome

CA125 was not mandatory in IOTA5, although it was highly encouraged. We expect missing values for CA125, for the following two reasons. First, following local protocols some centres were more committed than others to measure CA125. Second, the need to measure CA125 may depend on the overall clinical picture and the appearance of the tumour on ultrasound. Hence we expected clearly more missing values for cases that were followed up conservatively.

For some cases, as outlined above, the outcome is uncertain. The largest groups are cases without any information since the inclusion scan (U4 in the overview above), and cases with last FU <10 months after inclusion and without having had surgery and where the mass did not resolve spontaneously (U3).

Simply omitting cases with missing CA125 or outcome is likely to cause bias. For example, based on data from earlier IOTA studies, patients with missing CA125 have more often a benign tumor. The current data from IOTA5 indicate that CA125 is more often missing for patients that are followed conservatively than for patients that received surgery without follow-up visit. Further, we assume that conservatively followed patients with last follow-up <10 months will very often have a benign tumor.

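### A protocol sentence of unclear scope limits all analyses to women with a scan at one year or later, or complete history or surgical details; in time-to-event analyses it would bias surgery incidence upward

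*Protocol*

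**What the plan says.** The protocol's Duration of follow-up section ends with a paragraph on departments that take no part in management decisions. They cannot join the full study, but "In these centres data can be prospectively collected as an observational study". The next and last sentence is the rule at issue: "Only patients with appropriate outcome measures (i.e. follow up ultrasonography after one or more years". The alternative way in is a full record of the woman's history or operation. The reach is stated without limit: women who meet either condition "will be included in any statistical analysis".

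Other places bear on the same women:

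- **Protocol, Follow-up:** scans at 3 and 6 months, then "every 12 months (maximal range 10-14 months").
- **Protocol, Study screen, current status of the patient:** data are barred from analysis when consent is withdrawn. Nothing similar is said of women lost to follow-up.
- **Protocol, Statistical analysis, first objective:** "Patients that did not need surgery at the end of the follow-up period are right censored at the time of the last examination". No minimum follow-up is set.
- **Protocol, Statistical analysis, second objective:** a non-operated mass counts as benign at the first visit given "absence of a clinical diagnosis of cancer after 1 year of follow up".
- **2017 SAP, 1.2.1:** the survival analysis takes cases with at least one follow-up scan, whenever it took place.
- **2019 SAP, 1.3 and 1.5.1 to 1.5.2:** women with under 10 months of follow-up, or none, are labelled uncertain and their outcome is imputed in the primary analysis. The stated reason is "Simply omitting cases with missing CA125 or outcome is likely to cause bias".

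**The concern.** The sentence makes entry to an analysis depend on what happened after enrolment, and it treats events and non-events differently. Early surgery with recorded details qualifies a woman at once. An event-free woman must remain under observation for a year, unless her documented history happens to count as complete. In a survival analysis the second woman belongs in the denominator until she is last seen. Removing her shrinks the risk set and leaves the early operations in the numerator.

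The protocol analyses exposed to this are the Kaplan-Meier curve for need of surgery (objective 1) and the Cox-type analyses (objectives 2 and 3). Both SAPs are titled interim, so no supplied SAP governs the long-term analysis, and there the protocol sentence is the stated rule. Early loss is a realistic prospect: the 2017 SAP reports marked differences between centres in adherence to follow-up, and the 2019 SAP names women with short or no follow-up as the largest uncertain-outcome groups.

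**Working it through.** **Step 1. Set the rules side by side**

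| Woman | Protocol sentence, read literally | Protocol censoring rule | 2017 SAP survival set | 2019 SAP primary analysis |
|---|---|---|---|---|
| Followed from month 3, operated on at month 8, details recorded | In | Event | In | In, by histology (a malignancy found after 120 days may be uncertain and imputed) |
| Event-free, last scan month 8 | Out, unless her history counts as complete | Censored at month 8 | In, censored | In, outcome imputed |
| Event-free, last scan month 11, within the annual window | Out, unless her history counts as complete | Censored at month 11 | In, censored | In; outcome set by subjective assessment |

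The last row counts the annual scan from inclusion, as both SAPs do (24 plus or minus 2 months in one, 10 to 14 months in the other).

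**Step 2. Direction**

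The plan gives no event rate, loss rate or sample-size calculation, so there is no figure to reproduce. Scale time so that 12 months = 1, with surgery hazard L, resolution hazard H and loss hazard m, all constant and independent. With U = L + H + m:

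- A = (L/U)(1 − e^−U): surgery observed by 12 months
- R = (H/U)(1 − e^−U): resolution observed by 12 months
- B = e^−U: event-free and still followed at 12 months

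The true 12-month surgery incidence is L/(L+H) × (1 − e^−(L+H)). Under the sentence, with resolved women kept, the estimate is A/(A+R+B). Women lost before 12 months leave the denominator, so the estimate exceeds the true value whenever m > 0.

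**Step 3. Illustration**

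All inputs are assumptions: 16% surgery and 20% resolution by 24 months if each acted alone, and 10 to 40% lost by 12 months.

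- L = −ln(0.84)/2 = 0.0872; H = −ln(0.80)/2 = 0.1116; L + H = 0.1987
- True 12-month incidence = (0.0872/0.1987)(1 − e^−0.1987) = 7.9%

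| Lost by 12 months | A | R | B | A/(A+R+B) | Ratio to true |
|---|---|---|---|---|---|
| 10% | 0.0752 | 0.0962 | 0.7378 | 8.3% | 1.05 |
| 20% | 0.0711 | 0.0910 | 0.6558 | 8.7% | 1.10 |
| 30% | 0.0669 | 0.0856 | 0.5738 | 9.2% | 1.16 |
| 40% | 0.0624 | 0.0799 | 0.4919 | 9.8% | 1.25 |

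After month 12 the restriction removes nobody further. The 24-month value is therefore the 12-month estimate plus B/(A+R+B) × 7.9%: 14.7 to 16.0% against a true 14.4%.

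**Step 4. Vary the event risk**

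With surgery as the only event, the estimate is A/(A+B).

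- A true 12-month risk of 10% becomes 10.5%, 11.1%, 11.8% or 13.9% at 10%, 20%, 30% or 50% loss. At 20% loss: 0.0898/(0.0898 + 0.7200) = 11.1%.
- Across true risks of 2 to 20%, relative inflation is about 5% at 10% loss, 10 to 12% at 20%, 16 to 20% at 30% and 34 to 43% at 50%.

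**Step 5. The protocol's own estimator**

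Step 3 uses competing-risk incidence, but the protocol specifies Kaplan-Meier. With the Step 3 hazards and resolution treated as censoring, the true 12-month value is 1 − e^−0.0872 = 8.35%. In the restricted set the surgery hazard at time t is L·e^−Ut divided by [((L+H)/U)(e^−Ut − e^−U) + B]. Integrating it numerically over the year gives 8.75% at 10% loss and 10.55% at 40% loss, ratios of 1.05 and 1.26. The choice of estimator does not change the conclusion.

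**The case against.** **Scope.** The natural reading may be local: a minimum-data condition for departments that do not control follow-up. Those centres do not record suggested management, and the 2017 SAP selects on initial conservative policy, so on that reading the conflict with that SAP largely disappears. This stands as a limit on reach. It does not make the rule sound, because it would still select on outcome within those centres, and the wording names all analyses.

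**Contradiction.** The censoring rule says how women are censored, not who enters, so the two can formally coexist. That is fair: the protocol sentence is at odds with the censoring rule, because it removes women that rule would censor, but it does not negate it. The 2017 SAP also leaves out women without a follow-up scan and keeps immediate surgery out of its main survival analysis. The 2019 SAP excludes uncertain outcomes, though only as a sensitivity analysis.

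**Diagnostic objective.** One year of follow-up is part of how the protocol defines a benign non-operated mass, so a one-year requirement fits that definition. This stands, but it does not extend to the survival analyses.

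**Stronger readings.** A reader might infer that the whole study's incidence is inflated, or that women whose mass resolved early are also dropped. Under the Step 3 assumptions, dropping them would give A/(A+B) = 9.3 to 11.3% against 7.9%. The documents do not support either inference. Scope is unclear, the history criterion is undefined and may admit resolved women, and the study screen records resolution as a finding that needs no further detail. Nor do the interim analyses apply the sentence: both SAPs set other rules.

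**Conclusion.** The concern holds in limited form. As written, the sentence is a selection rule that biases surgery incidence upward in any time-to-event analysis to which it is applied, whether study-wide or only in observing departments. The direction needs only that early operations are kept and some early-censored women are dropped. The size is unknown. The 8.3 to 9.8% against 7.9% rests wholly on assumed constant hazards, independent loss and 10 to 40% loss by one year. The practical exposure is in later analyses run under the protocol rather than in the two interim SAPs. The point should be corrected, since following the stated rule gives a wrong answer and the correction is one sentence.

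**What to change.** Replace the last sentence of that paragraph with text to this effect:

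- State which centres the data-adequacy condition covers, and define what counts as complete history or surgical details.
- State that it does not restrict time-to-event analyses. These include all eligible consented women in the analysed centres, censored at the last examination.
- State that women with unresolved outcome enter the diagnostic analyses by the 2019 SAP's multiple imputation, with the outcome-complete set as a labelled sensitivity analysis.

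Selection of centres on data quality, as both SAPs do, can remain.

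The cost is a short protocol edit, more censored women and lower apparent completeness. No new data are needed.
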